4.3.3 Patient Identification

4.3.3.1 Patient's initials (first and last)

4.3.3.2 Patient's Hospital ID and/or Social Security number

4.3.3.3 Patient demographics

4.3.3.3.1 Gender

4.3.3.3.2 Birth date (mm/yyyy)

4.3.3.3.3 Race

4.3.3.3.4 Ethnicity

4.3.3.3.5 Nine-digit ZIP code

4.3.3.3.6 Method of payment

4.3.3.3.7 Country of residence

Rev. Add6
Rev. Add7

4.3.4 Additional Requirements

4.3.4.1 Peripheral blood specimens are required to be submitted for defined laboratory research studies as outlined in Section [10](#).

4.3.4.2 Peripheral blood specimens are to be submitted for future undefined research studies per patient consent as outlined in Section [10](#).

Rev. Add7

4.3.5 Stratification Factors

4.3.5.1 Clinical stage at diagnosis (II or III)

4.3.5.2 Residual cancer burden after neoadjuvant chemotherapy (1~3 cm or >3 cm)

4.3.5.3 Planned platinum agent (cisplatin or carboplatin)

4.3.5.4 Anthracycline exposure in the neoadjuvant setting (yes or no)

4.3.5.5 Administration of adjuvant radiotherapy (yes or no)

Rev. Add#5
Rev. Add8

4.3.6 Medidata Rave is a clinical data management system being used for data collection for this trial/study. Access to the trial in Rave is controlled through the CTEP-IAM system and role assignments.

Requirements to access Rave via iMedidata:

- A valid CTEP-IAM account; and
- Assigned a Rave role on the LPO or PO roster at the enrolling site of: Rave CRA, Rave Read Only, Rave CRA (LabAdmin), Rave SLA, or Rave Investigator.

Rave role requirements:

- Rave CRA or Rave CRA (Lab Admin) role must have a minimum of an Associate Plus (AP) registration type;

- Rave Investigator role must be registered as a Non-Physician Investigator (NPIVR) or Investigator (IVR); and
- Rave Read Only role must have at a minimum an Associates (A) registration type.

Refer to <https://ctep.cancer.gov/investigatorResources/default.htm> for registration types and documentation required.

Upon initial site registration approval for the study in RSS, all persons with Rave roles assigned on the appropriate roster will be sent a study invitation e-mail from iMedidata. To accept the invitation, site users must log into the Select Login (<https://login.imedidata.com/selectlogin>) using their CTEP-IAM user name and password, and click on the “accept” link in the upper right-corner of the iMedidata page. Please note, site users will not be able to access the study in Rave until all required Medidata and study specific trainings are completed. Trainings will be in the form of electronic learnings (eLearnings), and can be accessed by clicking on the link in the upper right pane of the iMedidata screen. If an eLearning is required and has not yet been taken, the link to the eLearning will appear under the study name in iMedidata instead of the Rave EDC link; once the successful completion of the eLearning has been recorded, access to the study in Rave will be granted, and a Rave EDC link will display under the study name.

Users that have not previously activated their iMedidata/Rave account at the time of initial site registration approval for the study in RSS will also receive a separate invitation from iMedidata to activate their account. Account activation instructions are located on the CTSU website, Rave tab under the Rave resource materials (Medidata Account Activation and Study Invitation Acceptance). Additional information on iMedidata/Rave is available on the CTSU members’ website under the Rave tab at www.ctsu.org/RAVE/ or by contacting the CTSU Help Desk at [name] or by e-mail at [contact].

4.3.7 ECOG-ACRIN Systems for Easy Entry of Patient Reported Outcomes (EASEE-PRO) System:

When patients consent to participate, they will be asked to provide a contact email address and that address along with their registration information will be sent directly from the parent trial’s registration system to EASEE-PRO, and the patient will be automatically registered into EASEE-PRO for participation. To activate their account for self-directed web entry of surveys, the system will send an activation message to the contact email address that will explain how to activate their account for self-directed web entry of surveys. After their account is activated, the patient will be able to complete questionnaires using a secure browser interface from any web enabled computer, tablet, or mobile device.

Rev. Add8

Rev. Add#5

Rev. Add#8

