2.2 Secondary Clinical Objectives

- 2.2.1 To evaluate OS and RFS in the two arms in patients with TNBC with residual basal-like disease after neoadjuvant chemotherapy.
- 2.2.2 To characterize the side effects and tolerability of each platinum agent (cisplatin and carboplatin) as well as capecitabine in patients with TNBC with residual disease after neoadjuvant chemotherapy.
- 2.2.3 To identify the rate of basal-like gene expression using PAM50 analysis by digital mRNA quantitation amongst drug-resistant residual TNBC after neoadjuvant chemotherapy.
- 2.2.4 To compare the IDFS in TNBC patients with residual non-basal-like disease after neoadjuvant chemotherapy who are randomized to post-preoperative platinum-based chemotherapy with those who are randomized to capecitabine (exploratory analysis).
- 2.2.5 To assess the difference in health-related quality of life (HRQL) between the platinum based and capecitabine chemotherapy arms.
- 2.2.6 To describe the rate of neurotoxicity over time in the platinum arm, the rate of medication adherence in the capecitabine arm and the rates of amenorrhea in both arms (exploratory).

Rev. Add7

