5.1.1 ARM B

Cisplatin 75 mg/m², IV infusion per institutional guidelines, day 1 every 3 weeks for a total of 4 cycles (12 weeks)

OR

Carboplatin AUC 6, IV infusion per institutional guidelines, day 1 every 3 weeks for a total of 4 cycles (12 weeks)

NOTE: CALVERT FORMULA FOR CARBOPLATIN DOSING:

Total Dose (mg) = (target AUC) x (GFR + 25)

For the purposes of this protocol, the GFR is considered to be equivalent to the creatinine clearance.

Glomerular Filtration Rate (GFR) Estimation: Calculated creatinine clearance of ≥ 50 cc/min using the Cockcroft-Gault formula:

Males:
$$\frac{(140 - \text{Age in years}) \times \text{Actual Body Weight in kg}}{72 \times \text{Serum Creatinine (mg/dL)}}$$

Females: Estimated creatinine clearance for females $\times 0.85$

With the Calvert formula, the total (final) dose of carboplatin is calculated in mg, not mg/m².

NOTE: Carboplatin maximum dose is based on a GFR estimate that is capped at 125 mL/min for patients with normal renal function. Based on Calvert formula, the recommended maximum AUC- based carboplatin dose is (or not to exceed or cap at):

AUC 6 \rightarrow 900 mg (max)

AUC 5 \rightarrow 750 mg (max)

AUC 4 \rightarrow 600 mg (max)

NOTE: Choice of platinum agent will be per treating physician discretion. Once a platinum agent is picked, no changes are allowed.

NOTE: In case of an event that causes a patient to reschedule appointments, treatment cycles should be no less than 19 days apart.

NOTE: All patients (on both arms) will be followed for development of recurrences, second primary cancer and survival based on standard ECOG-ACRIN following schedules (see Section [7](#) for details).

Rev. Add7
Rev. Add8

Rev. 9/17
Rev. Add#5

5.1.2 **ARM C**

Capecitabine 1,000 mg/m², PO twice daily, on days 1 - 14 every 3 weeks for a total of 6 cycles (18 weeks)

NOTE: In case of an event that causes a patient to reschedule appointments, treatment cycles should be no less than 19 days apart.

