9.2 Study Design

Based on the literature, the benefit of platinum agent therapy in TNBC after NAC, if any, is expected to be predominantly in the basal-like subtype. Hence, the primary population for the primary endpoint is the basal-like subtype in this trial. After screening, tumor tissue will be sent to EA CBPF for molecular profile via PAM50 analysis by digital mRNA quantitation (NanoString) in the residual surgical specimen to identify its molecular subtype. At the time when the trial was developed, we expected at least 75% of the residual post-NAC TNBC screened to fall within the basal-like subtype. Based on data available as of the 2019 Spring DSMC meeting, about 78% of the patients randomized to arms B and C fall in the basal-like subtype. We will use this proportion in the below sample size calculation. In addition, about 7% of patients screened had assay failure and their intrinsic subtype is unknown. We assume 7% of patients will have assay failure in the remaining patients as well.

After EA CBPF sending the confirmation of receipt of tumor tissue to EA Operations Office, all eligible patients will then be randomized according to the permuted block algorithm with a 1:1 randomization ratio to platinum and capecitabine arms. Stratification factors include 1) clinical stage at diagnosis (II or III), 2) residual cancer burden after NAC (1~3 cm or > 3 cm), 3) planned platinum agent (cisplatin or carboplatin), 4) anthracycline exposure in the neoadjuvant setting (yes or no), and 5) administration of radiotherapy (yes or no).

Since platinum is considered less toxic than capecitabine and also platinum is expected to be better than capecitabine on improvement of IDFS in patients with basal-like TNBC, a non-inferiority design with superiority alternative (a hybrid design³³ is preferred for this trial). The primary analysis for the primary endpoint will test the null hypothesis of inferiority of platinum. The sample size would be calculated based on a modest superiority alternative hypothesis. If the hypothesis of inferiority of platinum is rejected in the primary analysis, the secondary hypothesis of no difference vs. superiority of platinum will be tested. Due to the closed testing procedure, no multiple-comparison adjustment is required for the two hypothesis tests³⁴

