9.3.2 Toxicity

Another secondary endpoint of the study is to evaluate toxicities in patients with basal-like TNBC. All patients who start protocol therapy (i.e., receive at least one dose of protocol treatment) will be included in toxicity analysis. Assuming 14 basal-like TNBC patients (14/281=5%) will not start protocol therapy in each arm, with 267 evaluable patients, the binomial exact 95% confidence interval for toxicity rate would be no wider than 0.12, and there would be at least 83% power to detect a 13% difference in grades 3 or higher toxicity rate, using Fisher exact test with one-sided type I error rate of 0.025. For each individual platinum agent (carboplatin or cisplatin), the binomial exact 95% confidence interval for toxicity rate would be no wider than 0.17 if about the same number of patients (n=133) take each agent.

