Toxicity analysis will be conducted in all basal-like TNBC cases receiving at least one dose of chemotherapy (i.e., all treated population). Adverse events will be graded using the National Cancer Institute (NCI) Common Terminology Criteria for Adverse Events (CTCAE) version 4.0. All treatment-emergent and baseline adverse events and hematological/biochemical toxicities based on laboratory measurements will be summarized for patients on each arm. The incidence of deaths and treatment-emergent serious adverse events will be calculated along with exact 95% CI based on binomial distribution and compared between treatment arms using Fisher exact test. Also, the incidence of adverse events leading to discontinuation of chemotherapy and/or withdrawal from the study will be summarized and listed. Toxicity in all patients (including both basal-like and non-basal like patients) will be summarized and compared between treatment arms as well.

The proportion of basal-like TNBC in all screened TNBC patients will be calculated with exact 95% CI based on binomial distribution.

Rev. Add6

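### Planned platinum agent stratifies the randomization in both arms, but the toxicity plan does not use it, so each agent's randomized capecitabine control goes unused for tolerability

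*Combined protocol and SAP*

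**What the plan says.** - **Stratification.** Section 4.3.5 includes "Planned platinum agent (cisplatin or carboplatin") among five factors. Section 9.2 repeats the list and says eligible patients are "randomized according to the permuted block algorithm with a 1:1 randomization ratio to platinum and capecitabine arms".
- **Choice of agent.** Section 5.1.1: "Choice of platinum agent will be per treating physician discretion". It also bars a change of agent once one is picked.
- **Objective.** Section 2.2.2: "To characterize the side effects and tolerability of each platinum agent (cisplatin and carboplatin) as well as capecitabine".
- **Toxicity by agent.** Section 9.3.2: "For each individual platinum agent (carboplatin or cisplatin), the binomial exact 95% confidence interval for toxicity rate would be no wider than 0.17", on the supposition that about 133 patients take each agent. Only Arm B patients take a platinum agent, so this is a one-sample interval.
- **Toxicity by arm.** Section 9.3.2 claims at least 83% power for a 13-point difference in grade 3 or higher toxicity with 267 evaluable patients per arm (one-sided Fisher exact test, 0.025). In section 9.4, deaths and treatment-emergent serious adverse events are "compared between treatment arms using Fisher exact test". Neither section splits or stratifies the comparison by planned agent.
- **Efficacy.** The factor is used here: sections 9.2.1.2 and 9.4 stratify the Cox models and log-rank tests on the randomization factors.

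**The concern.** Patients planned for cisplatin form a randomized comparison of cisplatin with capecitabine. Patients planned for carboplatin form a second one. The objective is framed by agent, but the toxicity plan uses neither comparison.

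The stake is interpretive. Section 9.2 gives lower expected toxicity of platinum as one reason for the non-inferiority design. If platinum proves non-inferior but not superior, tolerability will carry much of the argument for using it. Sections 8.2.10 and 8.3.10 list different profiles for the two drugs: nephrotoxicity and ototoxicity are prominent for cisplatin, while thrombocytopenia and neutropenia lead the list for carboplatin. A pooled contrast could therefore hold for one agent and not for the other.

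A report showing a cisplatin rate, a carboplatin rate and one all-capecitabine rate invites side-by-side reading. Because physicians choose the agent, the two groups may differ at baseline, and that reading would mix drug effect with selection. The matched contrast avoids this.

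**Working it through.** **1. Is the control available?** The factor must be known before allocation, so it exists for every Arm C patient. Subtype is read from surgical tissue obtained before randomization, so restricting to basal-like patients does not undo the randomized basis. The documents contain no toxicity analysis by arm within planned agent.

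**2. The plan's own figures.** Section 9.3.2 says: "Assuming 14 basal-like TNBC patients (14/281=5%) will not start protocol therapy in each arm". This gives 281 − 14 = 267 per arm, and half of 267 is about 133 per agent.
- Power of the one-sided Fisher test (0.025) for 13 points, 267 per arm: the minimum over base rates is 83.6%, at 43.5% vs 56.5%. The stated figure of at least 83% is reproduced.
- Interval width per agent, n = 133: 2 × 1.96 × √(0.25/133) = 0.170. The stated 0.17 is reproduced, but by the normal approximation; the maximum exact (Clopper-Pearson) width is 0.176. Likewise at n = 267: 0.120 by approximation, 0.123 exact.

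**3. Precision of the matched contrast.** Half-width of a 95% interval for a difference, with an assumed rate of 40% in both groups (0.4 × 0.6 = 0.24):
- Whole arms, 267 vs 267: 1.96 × √(0.48/267) = 0.083, or 8.3 points.
- One stratum, 133 vs 133: 1.96 × √(0.48/133) = 0.118, or 11.8 points.
- At a 50% rate, where the interval is widest, the full width for 133 vs 133 is 2 × 1.96 × √(0.5/133) = 0.24.

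**4. Power within a stratum** (same Fisher test, 133 vs 133, 13-point difference):

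| Rates | Power |
|---|---|
| 10% vs 23% | 78% |
| 20% vs 33% | 63% |
| 30% vs 43% | 55% |
| 43.5% vs 56.5% (worst case) | 54% |

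About 80% power needs a difference of 17 to 18 points at mid-range rates (78% and 82%).

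**5. Sensitivity to the split.** The documents only suppose an even split. For other splits, half-width at a 40% rate is 1.96 × √(0.48/n):

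| Split | n per arm in stratum | Half-width (points) | Worst-case power, 13 points |
|---|---|---|---|
| 30:70 | 80 | 15.2 | 31% |
| | 187 | 9.9 | 69% |
| 20:80 | 53 | 18.7 | 19% |
| | 214 | 9.3 | 73% |

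**The case against.** The strongest reply is that the plan already does what its objective asks. Objective 2.2.2 is to characterize, and a rate with an interval among the patients given each agent does that. The documents plan no cisplatin-carboplatin contrast and no comparison of one agent with all of Arm C. The premise in section 9.2 concerns platinum as a class, and the adequately powered whole-arm comparison addresses it. Shared eligibility limits (creatinine clearance, neuropathy, performance status, marrow and liver function) also narrow how far the two groups can differ. Planned agent is on file, so the table could be produced at any time.

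Much of this stands, and it rules out three stronger readings that a reader might infer:
- *The per-agent rates are confounded.* They are not. Each is a valid description of the patients treated with that agent; confounding needs a contrast, and none is planned.
- *The Fisher comparison is biased because it ignores planned agent.* It is not. Allocation is 1:1 within planned-agent strata, so agent choice does not favour either arm. For deaths and serious adverse events, where counts may be small, an exact test is a sensible choice.
- *The bias from informal comparisons can be sized.* It cannot from these documents, which give no toxicity rate by planned agent.

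What the reply does not remove is that the trial stratifies by agent, has an objective by agent, and leaves the matched randomized contrast out of the toxicity plan. A table that can be made at any time is more credible if specified in advance.

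**Conclusion.** The point holds as a missed analysis, not as an error in a planned one. For tolerability, and only there, each agent's randomized capecitabine control is unused. The IDFS analysis is unaffected, and the factor already enters the efficacy models.

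The gain is an agent-specific difference largely protected from physician selection. The limit is precision: about 11.8 points either side at a 40% rate, against 8.3 for the whole arms, with power for the plan's 13-point target falling from at least 83% to about 54% in the worst case. These figures assume an even split; the smaller stratum does worse if the split is uneven. The contrasts therefore suit estimation rather than testing.

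One qualification remains. Toxicity is analysed in patients who start therapy, with 5% per arm assumed not to, in an open-label trial. The within-stratum contrast is close to randomized but not strictly intention-to-treat.

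**What to change.** In sections 9.3.2 and 9.4:
1. For each planned agent recorded at randomization, report the Arm B minus Arm C difference in grade 3 or higher toxicity with a 95% confidence interval. Label it as estimation in treated patients, without a power claim.
2. State that any cisplatin-carboplatin contrast is non-randomized. Do not set one agent's rate against the whole of Arm C.
3. Optionally, add an arm comparison stratified on planned agent as a supportive analysis, exact where counts are small. The planned Fisher tests can stay.
4. While editing section 9.3.2, correct the exact interval widths to about 0.123 and 0.176, or describe the stated 0.12 and 0.17 as normal-approximation values.

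The cost is some wording and a few tables; no new data are needed. The downside is wide intervals, possibly inconclusive in the smaller stratum, so the report should show the number of patients per arm in each stratum.

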4.4 Data Quality Portal

The Data Quality Portal (DQP) provides a central location for site staff to manage unanswered queries and form delinquencies, monitor data quality and timeliness, generate reports, and review metrics.

The DQP is located on the CTSU members' website under Data Management. The Rave Home section displays a table providing summary counts of Total Delinquencies and Total Queries. DQP Queries, DQP Delinquent Forms and the DQP Reports modules are available to access details and reports of unanswered queries, delinquent forms, and timeliness reports. Review the DQP modules on a regular basis to manage specified queries and delinquent forms.

The DQP is accessible by site staff that are rostered to a site and have access to the CTSU website. Staff that have Rave study access can access the Rave study data using a direct link on the DQP.

To learn more about DQP use and access, click on the Help icon displayed on the Rave Home, DQP Queries, and DQP Delinquent Forms modules.

Note: Some Rave protocols may not have delinquent form details or reports specified on the DQP. A protocol must have the Calendar functionality implemented in Rave by the Lead Protocol Organization (LPO) for delinquent form details and reports to be available on the DQP. Site staff should contact the LPO Data Manager for their protocol regarding questions about Rave Calendaring functionality.

Rev. Add#5

4.5 Instructions for Patients who Do Not Start Assigned Protocol Treatment

If after randomization a patient does not receive any assigned protocol treatment, baseline and follow-up data will still be collected and must be submitted through Medidata Rave and EASEE-PRO according to the schedule in the EA1131 Forms Completion Guidelines.

5. Treatment Plan

Rev. 6/16

5.1 Administration Schedule

Doses are based on actual body weight.

Arm A Observation closed to accrual in Addendum #3

Rev. 9/17

5.1.1 ARM B

Cisplatin 75 mg/m², IV infusion per institutional guidelines, day 1 every 3 weeks for a total of 4 cycles (12 weeks)

OR

Carboplatin AUC 6, IV infusion per institutional guidelines, day 1 every 3 weeks for a total of 4 cycles (12 weeks)

NOTE: CALVERT FORMULA FOR CARBOPLATIN DOSING:

Total Dose (mg) = (target AUC) x (GFR + 25)

For the purposes of this protocol, the GFR is considered to be equivalent to the creatinine clearance.

Glomerular Filtration Rate (GFR) Estimation: Calculated creatinine clearance of ≥ 50 cc/min using the Cockcroft-Gault formula:

Males:
$$\frac{(140 - \text{Age in years}) \times \text{Actual Body Weight in kg}}{72 \times \text{Serum Creatinine (mg/dL)}}$$

Females: Estimated creatinine clearance for females $\times 0.85$

With the Calvert formula, the total (final) dose of carboplatin is calculated in mg, not mg/m².

NOTE: Carboplatin maximum dose is based on a GFR estimate that is capped at 125 mL/min for patients with normal renal function. Based on Calvert formula, the recommended maximum AUC- based carboplatin dose is (or not to exceed or cap at):

AUC 6 \rightarrow 900 mg (max)

AUC 5 \rightarrow 750 mg (max)

AUC 4 \rightarrow 600 mg (max)

NOTE: Choice of platinum agent will be per treating physician discretion. Once a platinum agent is picked, no changes are allowed.

NOTE: In case of an event that causes a patient to reschedule appointments, treatment cycles should be no less than 19 days apart.

NOTE: All patients (on both arms) will be followed for development of recurrences, second primary cancer and survival based on standard ECOG-ACRIN following schedules (see Section [7](#) for details).

Rev. Add7
Rev. Add8

Rev. 9/17
Rev. Add#5

5.1.2 **ARM C**

Capecitabine 1,000 mg/m², PO twice daily, on days 1 - 14 every 3 weeks for a total of 6 cycles (18 weeks)

NOTE: In case of an event that causes a patient to reschedule appointments, treatment cycles should be no less than 19 days apart.

NOTE: Table below provides guidance on rounding the calculated dose of capecitabine as **only 500 mg tablets should be utilized. Please prescribe capecitabine based on the “number of 500 mg tablets” column as per table below, not based on the “total daily dose in mg” column.** Adjustments to capecitabine dose based on weight changes are not necessary unless there is ≥ 10% change in weight compared to baseline. Capecitabine tablets are to be swallowed whole, with water, 30 minutes after a meal. Tablets should not be cut or crushed. Dose escalations of capecitabine after dose reductions for safety are not permitted. Missed capecitabine doses beyond 3 hours of regular intake time should not be taken. In case of vomiting after capecitabine ingestion, dose should not be replaced. Please see Section [5.3](#) for additional information on capecitabine dose modifications.

| Guidelines for Capecitabine Dose Calculation According to Body Surface Area | | | | | | | | | |
|---|---------------------------------|---------------------------|---------------------------|--------------------------------|---------------------------|---------------------------|--------------------------------|---------------------------|---------------------------|
| BSA (m ²) | 100% Dose Level of Capecitabine | | | 75% Dose Level of Capecitabine | | | 50% Dose Level of Capecitabine | | |
| | 1000 mg/m ² (BID) | Number of 500 mg Tablets | | 750 mg/m ² (BID) | Number of 500 mg Tablets | | 500 mg/m ² (BID) | Number of 500 mg Tablets | |
| | Total Daily Dose (mg) | Morning Number of Tablets | Evening Number of Tablets | Total Daily Dose (mg) | Morning Number of Tablets | Evening Number of Tablets | Total Daily Dose (mg) | Morning Number of Tablets | Evening Number of Tablets |
| ≤ 1.25 | 2000 | 2 | 2 | 1600 | 2 | 1 | 1000 | 1 | 1 |
| 1.26 – 1.37 | 2600 | 3 | 2 | 2000 | 2 | 2 | 1300 | 2 | 1 |
| 1.38 – 1.51 | 2900 | 3 | 3 | 2300 | 2 | 2 | 1600 | 2 | 1 |
| 1.52 – 1.65 | 3300 | 3 | 3 | 2300 | 2 | 2 | 1600 | 2 | 1 |
| 1.66 – 1.77 | 3600 | 4 | 3 | 2600 | 3 | 2 | 1900 | 2 | 2 |
| 1.78 – 1.91 | 3800 | 4 | 3 | 2600 | 3 | 2 | 1900 | 2 | 2 |
| 1.92 – 2.05 | 4000 | 4 | 4 | 3000 | 3 | 3 | 2000 | 2 | 2 |
| 2.06 – 2.17 | 4300 | 4 | 4 | 3300 | 3 | 3 | 2300 | 3 | 2 |
| ≥ 2.18 | 4600 | 5 | 4 | 3600 | 4 | 3 | 2600 | 3 | 2 |

Rev. Add6

